## II. **SPECIFIC AIMS** (Research Objectives)

We hypothesize that the administration of methergonovine will be associated with a 1 point greater reduction in uterine tone (on a 0-10 scale) at 10 minutes after administration compared to carboprost.

1. The primary outcome will be the uterine tone score on a 0 to 10 scale 10 minutes after administering the study drug. A score of 0 will mean the uterus has 'no tone'. A score of 10 will mean there is 'excellent tone'.
2. Secondary outcomes will include:
  - a) change in uterine tone from the time of study drug administration to 5 minutes later,
  - b) administration of an additional uterotonic agent after the first study drug
  - c) number of transfused blood products within 24 hours from the time of delivery,
  - d) any surgical intervention intended to control bleeding: i.e. Bakri balloon, O'Leary stitch, d&e, exploratory laparotomy, B-Lynch sutures, hysterectomy or interventional radiology artery embolization,
  - e) intraoperative quantitatively measured blood loss (QBL),
  - f) pre-delivery to postpartum change in serum hemoglobin,
  - g) vasopressor requirement or hypovolemic shock
  - h) postpartum admission to the intensive care unit (ICU),
  - i) need for postoperative mechanical ventilation,
  - j) nausea, vomiting, or diarrhea, abdominal pain, shortness of breath, headache, blurred vision, anxiety, chest pain, sweating, or palpitations within 2 hours postpartum
  - k) hypertensive emergency (SBP>/=160 or DBP>/=110)
  - l) EKG changes indicative of myocardial ischemia,
  - m) acute renal dysfunction,
  - n) length of postoperative hospital stay,
  - o) postpartum acute lung injury or circulatory fluid overload in the context of blood product transfusion,
  - p) allergic reaction deemed the result of blood product transfusion

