## VI. BIOSTATISTICAL ANALYSIS

- a. Specific data variables being collected for the study (e.g., data collection sheets).

Baseline patient characteristics will be collected and documented on data collection sheets. These characteristics will include:

1. patient MRN
2. randomization group
3. age
4. height, weight, BMI
5. gravidity and parity
6. baseline hematocrit and platelet count measured at the time of admission or on the day of delivery

- b. Statistical methods

The balance of patient characteristics between the two groups before intervention will be evaluated using standardized differences. Shapiro-Wilk test will be used to confirm whether the primary endpoint, uterine tone score 10 minutes after drug administration, satisfies the normality assumption. Multiple linear regression will be conducted when normality assumption satisfied. In the case when the normality assumption is not established, log transformation/box-cox transformation of the outcome will be carried out before modeling. For secondary endpoints that are dichotomous, logistic regression will be used to

examine the intervention effect after adjusting for potential confounders. For continuous secondary endpoints, such as intrapartum blood loss, we will evaluate its distribution before performing appropriate modeling. Trial site will be included as a covariate in all models to adjust for the stratification of randomization by hospital.

c. Power analysis (e.g., sample size, evaluable subjects, etc.)

Assuming a common within-group standard deviation in uterine tone score of 1.9 points, a minimum sample size of 41 randomized patients per group would provide 80% power at a two-sided alpha level of 0.05 to detect a 1.2 point difference in mean uterine tone score at 10 minutes post secondary uterotonic administration between groups using a two-sample t-test. A total of 50 patients per group (100 patients total) will need to be randomized to account for protocol violations. Since we currently perform 175 C/S monthly at BWH, and approximately 20 patients undergoing non-emergent C/S receive methergine or hemabate for uterine atony each month, we anticipate needing to enroll 1250 patients in total to be able to randomize 100 patients to receive the study intervention.

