The within-group standard deviation estimate of 1.9 is based on the observed standard deviation in uterine tone score (averaged between raters) at 10 minutes post-delivery amongst patients in our previous study (The Inter-rater Reliability of a 0 to 10 Uterine Tone Score) who received a secondary uterotonic. The minimal clinically important difference of 1.2 points is based on the upper limit of the 90% confidence interval for the difference in uterine tone score (averaged between raters) at 3 minutes post-delivery between patients who did and did not receive a secondary uterotonic (difference in means [90% CI]: -2.3 [-3.5, -1.2]).

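### The protocol hypothesizes a 1-point difference but states 80% power only for 1.2 points, which it labels a minimal clinically important difference on the strength of a confidence limit; the SAP powers for 1 point only by assuming a smaller SD

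*Protocol*

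**What the plan says.** Protocol section II (Specific Aims) hypothesizes that methylergonovine will give a "1 point greater reduction in uterine tone (on a 0-10 scale) at 10 minutes after administration compared to carboprost". The Specific Aims of the Protocol Summary repeat the 1-point figure.

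Protocol section VI.c (Power analysis) uses a different target. "Assuming a common within-group standard deviation in uterine tone score of 1.9 points", it states that "a minimum sample size of 41 randomized patients per group would provide 80% power at a two-sided alpha level of 0.05". The difference to which this power refers is 1.2 points, compared by a two-sample t-test. It then adds: "A total of 50 patients per group (100 patients total) will need to be randomized to account for protocol violations". The Research Design and Methods section of the Protocol Summary repeats the 1.2 and 1.9.

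The same part of section VI gives the source of each input. For the SD: "The within-group standard deviation estimate of 1.9 is based on the observed standard deviation in uterine tone score (averaged between raters) at 10 minutes post-delivery", in women from an earlier study who had received a second-line drug. For the target: "The minimal clinically important difference of 1.2 points is based on the upper limit of the 90% confidence interval for the difference" at 3 minutes after delivery between women given and not given such a drug, reported as "difference in means [90% CI]: -2.3 [-3.5, -1.2"].

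The SAP's power statement has 37 per group, 80% power and two-sided alpha 0.05 for a 1-point difference with SD 1.5, also by two-sample t-test. It too plans 100 randomized. Its primary analysis adjusts for baseline tone and trial site.

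**The concern.** There are two linked problems.

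**The label on 1.2.** The limit of an interval nearest zero moves with the sample size and the confidence level. Clinical importance does not. The contrast also separates women who were given a second-line drug from those who were not, at 3 minutes after delivery. The trial compares two drugs among women who all receive one, 10 minutes after it is given. The documents offer no other basis for 1.2.

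**The power for the hypothesis.** The hypothesis and the SAP target 1 point, while the protocol's power section targets 1.2. The two documents also assume different SDs. Nowhere is power for 1 point given at SD 1.9, the value the protocol took from its own earlier data.

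Interpretation is at stake. If the trial finds no significant difference and its interval excludes 1.2, the label invites the conclusion that no clinically important difference exists, although the hypothesized 1 point could still lie inside the interval.

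**Working it through.** **Method.** For a two-sample t-test with n per group, difference d, SD s and two-sided alpha 0.05, the degrees of freedom are 2n − 2 and the noncentrality is d / (s√(2/n)). Power is the probability that the noncentral t falls beyond the 97.5% critical value in either direction.

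**Step 1: the plans' own figures.**
- Protocol, d = 1.2, s = 1.9, n = 41: noncentrality 1.2 / (1.9 × √(2/41)) = 2.86, power 80.7%. The smallest n that reaches 80% is 41, as stated.
- SAP, d = 1.0, s = 1.5, n = 37: noncentrality 1.0 / (1.5 × √(2/37)) = 2.87, power 80.8%. The smallest n is 37, as stated.

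Neither document has an arithmetic error.

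**Step 2: power for the hypothesized 1 point, unadjusted t-test.**

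| n per group | SD 1.9 (protocol) | SD 1.5 (SAP) |
|---|---|---|
| 37 | 61% | 81% |
| 41 | 65% | 85% |
| 50 | 74% | 91% |

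At SD 1.9 and 50 per group, for example, the noncentrality is 1.0 / (1.9 × 0.2) = 2.63 and power is 74.1%. With the 97 patients that remain after the 3 exclusions the SAP reports, power is about 73%. Reaching 80% at SD 1.9 takes 58 per group. The difference detectable with 80% power at SD 1.9 is 1.19 at 41 per group and 1.08 at 50.

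**Step 3: baseline adjustment.** Adjusting for a baseline score that has correlation r with the outcome reduces the residual SD to about 1.9√(1 − r²). Neither document gives r, so the values below are assumptions.

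| r | Residual SD | Power at 41 | Power at 50 |
|---|---|---|---|
| 0 | 1.90 | 65% | 74% |
| 0.3 | 1.81 | 69% | 78% |
| 0.5 | 1.65 | 78% | 85% |
| 0.6 | 1.52 | 84% | 90% |

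Power of 80% for 1 point needs r of about 0.54 at 41 per group, or about 0.37 at 50.

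**Step 4: how far the confidence limit depends on the earlier study.** The half-width of the reported interval is (3.5 − 1.2) / 2 = 1.15. Hold the estimate at 2.3 and the spread of the data fixed:
- a study half as large: 2.3 − 1.15 × √2 = 0.67
- a study four times as large: 2.3 − 1.15 / 2 = 1.73
- the same study with a 95% interval: 2.3 − 1.15 × 1.960 / 1.645 = 0.93

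These are illustrations, since the same estimate need not recur. By this route the claimed important difference could have been anywhere from about 0.7 to 1.7 with no change in clinical facts.

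**Step 5: an interval that excludes 1.2 but not 1.0.** With 50 per group and SD 1.9, the 95% half-width is 1.984 × 1.9 × 0.2 = 0.75. An observed difference of 0.4 would give −0.35 to 1.15, which excludes 1.2 and includes the hypothesized 1 point.

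**The case against.** The case on the other side has four parts.

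- **The power claim is true as worded.** The protocol claims 80% for 1.2 points and never for 1.0. This stands. A reader might infer that the stated power is wrong, but it reproduces.
- **The SAP powers for exactly 1 point.** A reader might infer from the protocol alone that the trial falls well short of 80% for its hypothesis. The documents do not support that without conditions. At SD 1.5 power is at least 81%. At SD 1.9 a large shortfall belongs to 37 or 41 per group, and at the planned 50 it is about 6 points before any gain from baseline adjustment. But the SAP gives no source for 1.5, and at 1.9 its 37 per group give 61%. Nor can 1.5 be taken as a baseline-adjusted version of 1.9. That would need r = √(1 − (1.5/1.9)²) = 0.61, and the SAP presents 1.5 as a within-group SD for an unadjusted t-test.
- **Receipt of a second drug is a clinical anchor.** It reflects a clinician's decision, and taking the limit nearest zero gives a smaller target than 2.3 and so a larger trial. This partly stands: 1.2 is weakly grounded as a planning value, not irrelevant. It does not make the limit a minimal clinically important difference.
- **No rule uses 1.2.** Neither document sets an equivalence margin or says results will be judged against 1.2, and the SAP does not mention it. This stands. The misreading is a risk created by the label, not a planned analysis.

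A reader might also infer that 1 point is the true clinical threshold. The documents give no clinical basis for 1 point either; it matters here because it is the stated hypothesis.

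**Conclusion.** The point holds as an unreconciled set of design assumptions together with a mislabelled target. The protocol hypothesizes 1 point and powers for 1.2 at SD 1.9; the SAP powers for 1 point at SD 1.5. Across 37 to 50 per group, power for the hypothesized difference is 61% to 74% under one SD and 81% to 91% under the other, so whether the trial has 80% power for its hypothesis depends on which SD is right.

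These figures assume equal groups, a two-sided alpha of 0.05, an unadjusted t-test and each SD at face value. Baseline adjustment would raise the SD 1.9 figures by an amount the documents do not allow one to calculate. The 1.2 is a usable planning difference but has not been shown to be a minimal clinically important one. The sample-size arithmetic is sound in both documents.

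**What to change.** 1. In protocol section VI.c, call 1.2 the planning (detectable) difference and drop the claim that it is a minimal clinically important difference.
2. Reconcile the target (1.0 or 1.2) and the SD (1.5 or 1.9) across the protocol, the Protocol Summary and the SAP, and give the source of the SD that is kept.
3. State power for the hypothesized 1 point under both SDs: 65% at 41 and 74% at 50 per group with SD 1.9; 85% and 91% with SD 1.5. Add that these are unadjusted figures, that the primary analysis adjusts for baseline tone, and that 80% at SD 1.9 would need a baseline correlation of about 0.54 at 41 per group or 0.37 at 50.
4. In reporting, do not read an interval that excludes 1.2 as showing no clinically important difference. Give the interval and say whether 1 point lies inside it.

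The cost is changes to wording and a less favourable stated power at SD 1.9. The 100 randomized need not change.

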## **VII. RISKS AND DISCOMFORTS**

Adverse reactions to methylergonovine include increased blood pressure, seizure, dizziness and headache, and nausea, vomiting, diarrhea and abdominal pain from uterine contractions. Rare effects include chest pain, myocardial infarction, coronary vasospasm, tachycardia, dyspnea, and hematuria. A large retrospective study of over 2 million parturients found no significantly increased risk of acute coronary syndrome or acute myocardial infarction after receiving methylergonovine. ACOG recommendations nonetheless state that methylergonovine should be avoided in patients with hypertension and cardiovascular disease.

The most common adverse reactions to carboprost include nausea, vomiting, diarrhea, as well as headache, myalgias, increased temperature and flushing. Due to its stimulation of smooth muscle contraction, modest increases in blood pressure may be seen, but these are generally clinically insignificant. Additionally, bronchospasm, abnormal ventilation-perfusion and hypoxia may occur, and may be particularly severe in patients susceptible to these complications. Carboprost is therefore contraindicated in patients with active asthma.

Patients with any contraindication to either of the study drugs will be excluded from participation in the study. Patients with a diagnosis of asthma will be interviewed to confirm if their asthma is active. Any patient who has used a bronchodilator within the past 24 months will be considered to have active asthma and will be excluded. If a patient carries a diagnosis of 'childhood asthma' and/or has not needed a bronchodilator for >24 months, they will be considered eligible to participate in the study. After enrollment, patients will be evaluated for all of the above side effects by a clinical investigator between at time of transfer to the postpartum floor and again between 18 to 24 hours after delivery. The obstetric 6-

week postpartum follow-up record will be reviewed by a clinical investigator to screen for thrombotic events or other side effects.

Administration of methylergonovine and carboprost will occur after delivery of the fetus. Single intramuscular doses of methylergonovine have been shown to decrease serum prolactin levels compared to women receiving placebo. However, milk production, rates of exclusive breastfeeding and infant weight gain have not been found to differ. Case reports indicate a possible association of methylergonovine with tachycardia, vomiting, diarrhea and agitation in the infant. A recent prospective observational study comparing postpartum use of methylergonovine with control found no difference in lactation or neonatal complications in the infants of mothers who received methylergonovine.

It is unknown whether carboprost is excreted in human milk and there are currently no studies determining the infant risk from carboprost in breastfeeding mothers.

No additional inpatient hospital time is anticipated by participating in this study.

## **VIII. POTENTIAL BENEFITS**

The potential benefits of receiving methylergonovine or carboprost during cesarean delivery include a reduction in PPH, a lower risk of transfusion requirement and other interventions used to control PPH.

On a population-based level, the potential benefit of this study lies in an improvement in our understanding and management of PPH by determining the superior second-line uterotonic between methylergonovine and carboprost. This in turn could lead to a significant decrease in maternal morbidity due to adverse events associated with PPH.

## **IX. MONITORING AND QUALITY ASSURANCE**

A physician investigator will be present during the entire consent, enrollment and conduct of the study. Criteria for early termination from the study will be observed. Two definitions of early endpoints will be utilized:

1. Subject decision for withdrawal from participation at any time.
2. Any operative or medical condition changes prior to or during the entire study period deemed unacceptable by the obstetrician, anesthesiologist, or physician investigator.

The principal investigator will review all forms and data with every 5th subject to ensure completeness, accuracy and adherence to the protocol. There will be no data safety monitoring board (DSMB) in this study. In place of a DSMB, the Principal Investigator will take full responsibility for standardized review of recruitment at the above frequency, to ensure adherence to protocol, detection of minor or major adverse events (AE's), and timely reporting of such events to the IRB with halting of the study if necessary (for any AE's).

All AE's, whether or not they are considered related to the study, shall be recorded on the Adverse Experience Form within the Case Report Forms (CRFs). The study investigators will comply with the Food and Drug Administration (FDA) regulations requiring the expedited reporting of any AE that is Serious, Unexpected, and Associated with the use of the study drug. AEs will be reported to the PHRC in accordance with the PHRC Policy on Unanticipated Problems Involving Risks to Subjects or Others, including Adverse Events.

Serious AE's include hemodynamic instability requiring epinephrine or norepinephrine or resulting in loss of consciousness or cardiovascular collapse, allergic or anaphylactic reactions to study solution infused, major respiratory complication during hospital admission, or seizure activity. Should any of these events occur, the Principal Investigator will be contacted immediately, the study code broken, and the case reviewed. Serious AE's that occur higher than the expected native incidence will warrant temporarily halting the study and consultation with the Directors of Obstetric Anesthesia ([name]) and Labor and Delivery ([name]).

The standard causality criteria will be used to determine these AE's. Investigators will notify the principal investigator immediately of all SAEs. If necessary, any additional relevant information will be collected and reported. All AE's will be reported to the IRB per the HRC guidelines.

**Please DO NOT access the patient's record prior to completing this form!**

Did the patient have any of the following before transfer to the postpartum floor?

	YES	NO
Nausea?		
Vomiting?		
Diarrhea?		
Shortness of Breath?		
Headache?		
Blurred Vision?		
Severe Anxiety?		
Chest Pain?		
Abnormal Sweating?		

Patient Name: \_\_\_\_\_

MRN: \_\_\_\_\_

Study Number: \_\_\_\_\_

Date/Time of Interview: \_\_\_\_\_

Questions or Concerns:

[name]  
e: [contact]  
pg: [name]

Page 62 of 99

**2-4 HR POSTPARTUM  
BLINDED INTERVIEW GUIDE  
SECOND-LINE UTEROTONICS in PPH STUDY**

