Within the first 24 hours after delivery, but no sooner than the time of patient transfer from the labor and delivery floor to the postpartum unit, Between 2-4 hours postpartum and again between 18-24 hours postpartum, a blinded study investigator who is not involved in the subject's clinical care will interview the patient by phone (to avoid physical contact and minimize the risk for COVID-10 transmission) and record the information from the interview on the corresponding '2-4 Hr Interview Guide' or '18-24 Hr Interview Guide'. This will allow them to assess subjective side effects of the study medication such as G.I. upset, dizziness, shortness of breath, palpitations or chest pain. Non-English speaking patients will be interviewed in person with the assistance of an in-person interpreter from BWH Interpreter Services.

Subject randomization, patient MRN and the linked study ID number will be documented on a separate form in the secure electronic database, REDCap database by the unblinded principal investigator. This form will be visible only to the principal investigator. An unblinded study investigator (i.e. the principal investigator, or a research assistant, when one is hired in the future) with access to REDCap will be responsible for collecting and entering all primary and secondary outcomes from the Uterine Tone Score Intraop Data Collection sheet, the 2-4 Hour Interview Guide and the 18-24 Hour Interview Guide and Epic medical records (including side-effects of study medications) into REDCap. Subject randomization will be documented, on a separate form in the database to which only the principal investigator has access, in order to preserve the integrity of the data collection and entry.

The need for blood product administration and quantity of each component given within 24hrs after cesarean section will be recorded. In addition, the investigator will record any additional interventions performed to halt bleeding, such as Bakri balloon placement, B-Lynch sutures, uterine artery embolization or hysterectomy.

Total intravenous fluids given from start to conclusion of the delivery will be recorded. The use of vasopressors, uterotonic agents, anti-emetic agents will be recorded. Length of stay and any postoperative complications occurring during the hospital stay will be documented at the time of hospital discharge.

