At the end of the C/S, the anesthesiologist will return the Randomization sheet and the Uterine Tone Score Intraop Data Collection sheet in the previously sealed envelope to a folder where all paper documents for the study are temporarily stored in a locked room on the L&D floor. On each day of subject enrollment, the unblinded principal investigator will collect the envelope with the Randomization sheet and Uterine Tone Score Intraop Data Collection sheet and transfer it to a locked filing cabinet in a locked office to which only the principal investigator has access.

After the subject has recovered on the L&D floor and is ready for transfer to the postpartum floor, a blinded study co-investigator will interview the patient by phone (to limit physical contact, due to COVID-19 precautions)

using the '2-4 Hour Interview Guide'. At 18-24 hours postpartum, the subject will again be interviewed by phone by a blinded study co-investigator, using the '18-24 Hour Interview Guide'. Both postpartum interview guides will contain the same content, allowing for subjective adverse effects to be accurately assessed at 2 timepoints. (no later than 24 hours after delivery). This data will be documented on the 2-4 Hour and 18-24 Hour Interview Guides, to be retrieved by the principal investigator (who is not blinded) after the day of subject enrollment, then stored in the locked office, and ultimately entered into a secure electronic database, REDCap, by a blinded study investigator. This will allow them to assess for any subjective side effects of the study medication, as listed below (Secondary Endpoint #9).

An unblinded study investigator not involved in data collection and with access to REDCap will be responsible for collecting all primary and secondary outcomes (including side-effects of study medications) from the Uterine Tone Score Intraop Data Collection sheet, the Pre Transfer Interview Guide and Epic medical records onto the Second Line Uterotonics Data Collection Sheet and entering this information into REDCap. Subject randomization, patient MRN and the linked study ID number will be documented on a separate form in the REDCap database by the unblinded principal investigator, to preserve the integrity of the data collection and entry.

Study endpoints will be:

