#### Secondary Endpoints

1. Uterine tone score recorded at 5 minutes following the administration of the second-line uterotonic.
2. Need for an additional uterotonic agent after the study drug
3. Number of units of blood products transfused ( $t_0$  = time of delivery;  $t_{final}$  = 24 hours after delivery)
4. Need for a surgical or radiologic intervention to control bleeding
5. Quantitative intrapartum blood loss
6. Pre- vs post-delivery hematocrit values
7. Maternal morbidity: vasopressor requirement or hypovolemic shock, admission to the intensive care unit postpartum, mechanical ventilation, hypertensive emergency, myocardial ischemia, acute kidney injury, acute lung injury or circulatory overload from blood transfusion, allergic reaction deemed the result of blood transfusion, hypovolemic shock, or vasopressor requirement.
8. Length of postoperative hospital stay

9. Medication side effects within 2 hrs postpartum: nausea, vomiting or diarrhea, abdominal pain, shortness of breath, headache, blurred vision, anxiety, chest pain, sweating, palpitations

For studies involving treatment or diagnosis, provide information about standard of care at Partners (e.g., BWH, MGH) and indicate how the study procedures differ from standard care. Provide information on available alternative treatments, procedures, or methods of diagnosis.

All patients undergoing a C/S delivery at the Brigham and Women's Hospital (BWH) have a peripheral IV and baseline laboratory work on admission to the labor and delivery floor. The standard of care at BWH for women undergoing C/S includes spinal anesthesia with bupivacaine, fentanyl, and morphine, as will be used in this study unless contraindicated. The overall anesthetic management of a patient in the operating room will be at the discretion of the anesthesia attending physician, including crystalloid fluid administered, anti-emetic medication, analgesic medication and vasopressors used. Blood products transfused will be at the discretion of the attending physicians.

At the time of C/S and clamping of the umbilical cord, a standard infusion of oxytocin 30U/500mL is begun at a rate of 15-30U/hr. If uterine tone is perceived to be inadequate, this rate may be increased and the obstetrician may attempt maneuvers to improve uterine tone. Additionally, at this time a second-line uterotonic is typically requested.

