All continuous secondary outcomes were initially assessed for the normality of residuals from a multivariable linear regression model with trial site and baseline uterine tone as covariates. Outcomes displaying normally distributed model residuals were analyzed using multivariable linear regression, with effect size presented as adjusted difference in means with 95% CI. Outcomes with all non-zero values that displayed skewed linear regression model residuals were natural log-transformed and analyzed using multivariable linear regression, with effect size presented as adjusted ratio of geometric means with 95% CI. Outcomes containing at least one zero value that presented skewed linear regression model residuals were compared between groups using multivariable quantile regression, with effect size presented as adjusted difference in medians with 95% CI.

All binary outcomes were initially considered for comparison using multivariable logistic regression (for single measurements) or generalized estimating equations with a logit link (for repeated measurements) with trial site and baseline uterine tone as covariates. If the multivariable regression converged, effect size was presented as adjusted odds ratios with 95% CI. If the model did not converge due to low incidence, groups were compared using a Fisher's exact test and effect size presented as risk difference with exact 95% CI.

Time to receive second study drug was compared between groups using a multivariable Cox proportional hazards model, with effect size presented as adjusted hazard ratio with exact 95% CI. Complete-case analysis was performed for all secondary outcomes. All analyses were performed using SAS software version 9.4 (SAS Institute, Cary, NC).

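### The side-effect endpoint lists anxiety of any degree, but both interview guides and the data collection sheet record only severe anxiety, so that component cannot be reported as defined

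*Protocol*

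**What the plan says.** The Detailed Protocol, II. Specific Aims, secondary outcome (j), defines the side-effect endpoint as "nausea, vomiting, or diarrhea, abdominal pain, shortness of breath, headache, blurred vision, anxiety, chest pain, sweating, or palpitations within 2 hours postpartum". The Protocol Summary, Secondary Endpoints, item 9, gives the same symptoms, ending "headache, blurred vision, anxiety, chest pain, sweating, palpitations". Neither list attaches a severity to anxiety.

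The two postpartum interview guides attached to the protocol each have nine Yes/No items. The anxiety item on both reads "Severe Anxiety", and the sweating item reads "Abnormal Sweating". The Protocol Summary, Research Design and Methods, confirms that the two forms are meant to be alike: "Both postpartum interview guides will contain the same content". The data collection sheet at the end of the Detailed Protocol has an anxiety column restricted to severe in the same way. Its sweating column is headed diaphoresis, with no qualifier.

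The interviews are not the only source. V. Study Procedures also draws on "Epic medical records (including side-effects of study medications"), and the Protocol Summary has these data transferred to the data collection sheet before entry into REDCap.

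The SAP defines no side-effect composite. Its general rule is "All binary outcomes were initially considered for comparison using multivariable logistic regression", with Fisher's exact test where a model fails to converge because events are few.

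**The concern.** The form sets a higher bar than the endpoint for one symptom. Asked as written, a woman who felt moderately anxious after the study drug should answer No, although the protocol counts her as having the side effect. A Yes/No answer on a severe-only question holds no information about milder anxiety, so the gap cannot be closed at analysis.

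Tolerability helps to decide which of two otherwise interchangeable drugs is preferred, and the carboprost label reproduced in the protocol lists both nervousness and anxiety among its adverse effects. If the result is published under the endpoint's name, readers will take a severe-anxiety rate for an anxiety rate. They could also read the absence of a difference in severe anxiety as evidence about anxiety in general.

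**Working it through.** The plan states no figure on this point, so there is none to reproduce. The check sets the endpoint list against the forms, item by item.

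| Endpoint symptom (aim j; Summary item 9) | Both interview guides | Match |
|---|---|---|
| Nausea | asked, unqualified | yes |
| Vomiting | asked, unqualified | yes |
| Diarrhea | asked, unqualified | yes |
| Shortness of breath | asked, unqualified | yes |
| Headache | asked, unqualified | yes |
| Blurred vision | asked, unqualified | yes |
| Chest pain | asked, unqualified | yes |
| Anxiety | severe only | no, narrower |
| Sweating | abnormal sweating | arguable |
| Abdominal pain | no item | missing |
| Palpitations | no item | missing |

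Count: 7 matching + 2 qualified + 2 missing = 11 endpoint symptoms, and 7 + 2 = 9 guide items.

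**Anxiety.** The threshold is not a general rule of the form, because seven other symptoms are asked as present or absent. The two guides and the sheet agree with each other and differ from both endpoint statements. No section explains the restriction.

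**Whether chart abstraction repairs it.** Milder anxiety may be noted in the medical record. But the abstracted data go onto the data collection sheet, whose only visible anxiety column is the severe one. As written, there is nowhere to put such a finding.

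**Sweating.** The sheet's column is diaphoresis without a qualifier. The guide's wording reads naturally as the lay form of that term. This is not a clear mismatch.

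**Abdominal pain and palpitations.** Neither guide has an item, although V. Study Procedures says the interview assesses palpitations. Neither has a visible column on the sheet. The sheet's layout is broken in the available text, so its absence there is less certain than the absence from the guides.

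**How far the size depends on assumption.** Suppose any anxiety occurs in 30% and 15% of 50 women per arm, or in 40% and 20%, and that a share *s* of it is severe. Expected events recorded are 50 × rate × *s*. Power is for a two-sided Fisher's exact test at 0.05, computed exactly.

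| *s* | Events, 30% vs 15% | Power | Events, 40% vs 20% | Power |
|---|---|---|---|---|
| 1 (any anxiety) | 15.0 vs 7.5 | 35% | 20.0 vs 10.0 | 52% |
| 0.80 | 12.0 vs 6.0 | 26% | 16.0 vs 8.0 | 39% |
| 0.60 | 9.0 vs 4.5 | 17% | 12.0 vs 6.0 | 26% |
| 0.30 | 4.5 vs 2.25 | 5% | 6.0 vs 3.0 | 9% |
| 0.15 | 2.25 vs 1.125 | 1% | 3.0 vs 1.5 | 2% |

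The share of defined events recorded as absent is simply 1 − *s*, so it restates the assumption. The table shows the direction of the effect (fewer events, less power). It does not measure the loss in this trial.

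**The case against.** The strongest reply is that little is lost. Limiting a non-specific symptom to severe cases can be a deliberate choice, and changing the endpoint's label to severe anxiety would settle the inconsistency without touching a form. The trial is sized on uterine tone, so a comparison of any single symptom is weak under either wording: even the unqualified item has only 35% to 52% power for a doubling of risk under the assumptions above. All of this stands. It limits the weight of the point, but it does not make the form agree with the endpoint.

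A reader might infer more than the documents support, in four ways:

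- *That the whole side-effect endpoint is lost.* It is not. Seven of the 11 symptoms are asked in matching terms, and the SAP defines no composite that one faulty component could spoil.
- *That sweating has the same defect.* The diaphoresis column on the sheet makes the guide's wording a plausible plain-language version of the endpoint term.
- *That the comparison between drugs is biased.* The same item is put to women in both arms by an interviewer who is to be blinded. The documents show a narrower measurement and fewer events. They do not show a distortion favouring one drug.
- *That the wording removes most of the events or the power.* That follows only if a small severe share is assumed, and the documents give neither an anxiety rate nor a severe share.

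Only one of the two attached guides carries a visible 2-4 hour title, and it is uncertain which page that title heads. The items are identical on both, so nothing turns on it.

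**Conclusion.** The inconsistency is real for anxiety. Two endpoint statements count anxiety of any degree, while two interview guides and the data collection sheet record only severe anxiety. Followed as written, the plan under-counts this component and would report it under the wrong name, and chart abstraction does not clearly repair it.

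The size is small: one of 11 secondary symptoms, no demonstrated bias between arms, and a loss that cannot be quantified from the documents. The conclusion assumes that interviewers ask the item as printed and that the sheet has no further anxiety column hidden by its broken layout. It is a minor correction, worth making because it changes what may be concluded about anxiety and costs almost nothing.

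**What to change.** **If the forms can still change.** On both guides and the data collection sheet, ask 'Anxiety?' (Yes/No), followed by 'if yes: severe?'. The component as defined and the severe subset are then both available. In the same revision, add Yes/No items for abdominal pain and palpitations. The sweating item can stay.

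**For women already interviewed, or if the forms are closed.** Label and report the item as severe anxiety in tables and text. Do not pool it with the new item, and draw no conclusion about anxiety in general. This may be the only route left, because the SAP is written in the past tense and already counts patients with missing tone scores. In that case, also state that abdominal pain and palpitations were not asked about in the interviews.

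**Cost.** One item reworded with a follow-up tick, two items added to existing forms, and notification of the IRB. Earlier and later interviews will not be directly comparable on anxiety. Relabelling alone costs a line in the analysis and the report.
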